Another important aspect in childhood obesity interventions is their intensity and duration. In this sense, medium-high intensities and longer durations have been associated with greater efficacy (Whitlock, O'Connor, Williams, Beil, & Lutz, 2010). Specifically, Kitzmann et al.'s (2010) review noted that with an intervention duration of around four months, the results obtained were as effective as with more extensive interventions.

Adherence to treatment is another crucial aspect in the treatment of obesity. There are studies that define which variables predict the drop-out of treatment, such as the bad relationship between parents and the child, the lack of time and motivation, the coincidence with other academic activities, the high level of family stressors, and the distance between the home and the center where the intervention is being carried out (Brennan, Walkley, & Wilks, 2012; Moroshko, 2011; Braet, Jeannin, Mels, Moens, & Van Winckel, 2010; Barlow & Ohlemeyer, 2006).

Other relevant factors that predict greater treatment effectiveness are variables such as age and gender (Moens et al., 2010; Goossens, Braet, Van Vlierberghe, & Mels, 2009), placing adolescence as a more difficult stage in which to achieve changes. Other variables include psychological problems during childhood (Moens et al., 2010; Epstein, Klein, & Wisniewski, 1994) and the degree of parental motivation (Gunnarsdottir et al., 2011; Braet et al., 2010; Moens, Braet, & Van Winckel, 2010; Braet, 2006). Despite taking into account all the previously described variables, the vast majority of treatments have focused on long-term weight reduction as the sole objective of intervention, leaving aside all these psychological and family correlates that maintain the problem.

Objetive

The main objective is to examine the effectiveness of the intervention program 'ENTREN-F' (intervention for children plus family intervention) on anthropometrics, behavior, psychological and family factors, from a multidisciplinary perspective, compared with another group participating in the same program 'ENTREN' (intervention for children without family intervention) and with a control group (usual treatment) among Spanish children with over-weight and obesity. Finally, the second aim was to evaluate whether the changes were maintained 6, 12 and 18 months after the end of the intervention.

Hyphotesis

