The specific hypotheses of the present study were as follows: (a) There will be significant differences in the adherence to treatment, being higher in the ENTREN-F group (b) There will be improvements in clinical outcomes regarding the anthropometric variables of the child, the level of physical activity, psychological distress, and eating disorder of the child, after both interventions (ENTREN and ENTREN-F programme), in comparison to control group (d) There will be only improvements in clinical outcomes regarding in the family's healthy life-style, psychological distress of the parents, and the family environment, after the intervention of the ENTREN-F programme. (e) The significant changes produced will remain stable at the 6, 12 and 18-month follow-up in the ENTREN-F group.

Method

Participants and Recruitment Procedure

The sample will be made up of 240 children of 8-12 years old (IMC>P90). The dropout rate is expected to be 20%. The majority of the participants will be recruited through Primary Health Care Services, in collaboration with Pediatrics Area. Another percentage of the sample contacted the program after receiving information from their school or advertising posters.

Participation was voluntary and informed assent and consent was obtained by each participating family. Participants were told that the personal content of session discussions was confidential and should not be discussed outside the sessions.

Participants were randomly assigned to either (a) the psychofamily-based workshop program (ENTREN-F), (b) the only psychological workshop program (ENTREN) or (c) the Control Group. Participants were asked to complete questionnaires at baseline prior to the intervention (T_0) , at the end of the intervention and (T_1) , at 6-month follow-up (T_2) , at 12-month follow-up (T_3) and at 18-month follow-up (T_4) .

Design and contents

ENTREN Programme (experimental)

This intervention consists in a total of 12 biweekly sessions: 9 sessions of 2-hr only for children, with a further three 3-hr sessions attended by both families and children together: nutrition, physical activity sessions, and a closing event session. Los contenidos

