de las sesiones con los niños se basan en una perspectiva cognitivo-conductual e incluyen estrategias de la entrevista motivacional. El objetivo de las sesiones con los niños es trabajar la conciencia del problema, la motivación al cambio, el concepto de salud, la regulación emocional, las habilidades sociales y autoestima. One 2-hr sesión at 6, 12 and 18-month follow-up was provided to refresh skills, their physical activity, and nutritional behaviours.

ENTREN-F Programme (experimental)

ENTREN-F has the same children's intervention than ENTREN. It has extra 6 2-hr sessions to work on family environment and communication, plus three 2-hr sessions attended by both families and children together. One 2-hr sesión at 6, 12 and 18-month follow-up was provided to refresh skills, their physical activity, and nutritional behaviours.

Control Group Programme

The intervention of this group consists in usual treatment in Primary Care provided by Endocrinology Services. 3 monthly face-to-face consultations and continous online monitoring are provided to these families, oriented to promote healthy habits of nutrition and physical activity for 6 months. It works from an exclusively behavioral perspective. We used a *token economy*, a system of contingency management based on the systematic reinforcement of target behavior.

Instruments

• Anthropometric variables

Nurses measured children and parents: height, weight, waist circumference and middle arm circumference. Mother and children's Body mass index (BMI) has been calculated. Participating children's BMI Z-scores was calculated according to the age and specific sex, according to the median and standard deviation, based on the data collected in the Growth Tables of Orbegozo Foundation (Sobradillo et al., 2004).

• Lifestyle habits

Actigraph, model GT3X. The Actigraph (Actigraph TM, LLC, Fort Walton Beach, FL, EE.UU) is a small and lightweight triaxial activity monitor/accelerometer (4,6 x 3,3 x 1,5

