## **Statistical Analysis Plan (SAP)**

The statistical considerations for analyzing the data collected in the study are detailed below:

First, analyses will be carried out with the SPSS 26.0 version (IBM, SPSS, 2019).

Descriptive statistics (means, standard deviations, and percentages) of all the sociodemographic, clinical, and psychological variables will be calculated. A Shapiro–Wilk test will be used to check normal distribution.

Participant BMI changes over time by group will be measured using a Kruskal-Wallis test.

To carry out the comparisons, two-way analysis of covariance (ENTREN-F, ENTREN, Control Group) and time (T0,T1, T2 and T3) will be used.

Mixed model repeated measures analyses of covariance models tested whether intervention effects varied for each type of group.

In those cases in which we found significance in the global comparisons, we will carried out pairwise comparisons following asignificant main effect of time (post hoc Bonferroni test).

Finally, the effect size will be measured using partial eta squared ( $\eta$ 2), which estimates the degree of association for the sample. The guidelines for interpreting this value are as follows:  $\geq$ 0.14, large effect;  $\geq$ 0.06, medium effect;  $\geq$ 0.01, small effect (Cohen, 1988). The value P<0.05 was considered as a significant difference.

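### No between-arm analysis in the SAP allows for workshop clustering; if the ENTREN programmes run in workshops nested within arm and the within-workshop ICC is positive, p-values are too small

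*SAP*

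**What the plan says.** The protocol (Participants and Recruitment Procedure) randomises individual participants to three arms and names two of them as workshops: "the psychofamily-based workshop program (ENTREN-F), (b) the only psychological workshop program (ENTREN"). ENTREN is described as "9 sessions of 2-hr only for children, with a further three 3-hr sessions attended by both families and children together". ENTREN-F has the same children's intervention, plus six family sessions and three joint sessions. On confidentiality the protocol says: "Participants were told that the personal content of session discussions was confidential and should not be discussed outside the sessions". Control is different in kind: "3 monthly face-to-face consultations and continous online monitoring are provided to these families".

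The SAP lists three between-arm analyses:
- for BMI, "Participant BMI changes over time by group will be measured using a Kruskal-Wallis test";
- for the comparisons in general, "two-way analysis of covariance (ENTREN-F, ENTREN, Control Group) and time (T0,T1, T2 and T3) will be used";
- and "Mixed model repeated measures analyses of covariance models tested whether intervention effects varied for each type of group".

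Bonferroni pairwise comparisons follow a significant global result. The SAP text available mentions no workshop, session leader, ICC or cluster-robust variance, and gives no random-effects structure for the mixed model. The protocol gives no workshop size or number, and does not say whether the two ENTREN arms attend child sessions together.

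**The concern.** Children who attend the same workshop share a leader, a peer group and a set of discussions, so their outcomes after baseline may be correlated. Repeated-measures terms deal with correlation within a child, not between children. Kruskal-Wallis assumes independent children and cannot take a random effect. If correlation exists and is ignored, the standard error of an arm difference is understated.

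The Objective sets ENTREN-F against the programme without family intervention ("compared with another group participating in the same program") and against control. The first contrast isolates the added family sessions. If workshops are nested within arm, both sides of it are clustered, so it is the most exposed of the three.

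**Working it through.** **Inputs from the documents.** 240 children; 20% dropout; three arms; significance at P<0.05. The figure of 240 comes with no power, effect size or SD, so there is no calculation to reproduce, and it is not called wrong here.

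**Assumptions not in the documents.** 1:1:1 allocation, giving 240 × 0.8 / 3 = 64 completers per arm; workshops of m = 8 completers (8 per ENTREN arm); control unclustered; two-sided tests; ICC from 0 to 0.10, as a share of post-baseline variance.

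**Workshops nested within arm, one time point.** Design effect DE = 1 + (m − 1) × ICC. True size of a nominal 5% test = 2[1 − Φ(1.96/√V)], with V = DE when both arms are clustered and V = (1 + DE)/2 when one is.

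| ICC | DE | ENTREN-F vs ENTREN | Workshop arm vs control |
|---|---|---|---|
| 0 | 1.00 | 5.0% | 5.0% |
| 0.01 | 1.07 | 5.8% | 5.4% |
| 0.05 | 1.35 | 9.2% | 7.1% |
| 0.10 | 1.70 | 13.3% | 9.2% |

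With 6 to 12 completers per workshop at ICC 0.05, DE is 1.25 to 1.55 and the sizes are 8.0–11.5% and 6.5–8.3%. Simulation at m = 8 and ICC 0.05 gave 9.0% and 7.0% for the two comparisons, 8.5% for the three-arm F test and 8.4% for Kruskal-Wallis.

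**Bonferroni pairwise test.** For three arm pairs the nominal level is 5%/3 = 1.67%, critical value 2.394. At ICC 0.05 the size for ENTREN-F vs ENTREN is 2[1 − Φ(2.394/√1.35)] = 3.9%.

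**Change from T0.** If the workshop effect arises only after T0, the ICC of change is ICC/(2 − 2r), where r is the T0–T1 correlation. ICC 0.05 gives 0.05 at r = 0.5 and 0.125 at r = 0.8, so DE is 1.35 and 1.875, and the size for ENTREN-F vs ENTREN is 9.2% and 15.2%. Simulated three-arm Kruskal-Wallis on change gave 8.8% and 14.5% at ICC 0.05, and 5.9% and 6.7% at ICC 0.01.

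**Child workshops shared by both ENTREN arms** (four children from each arm in a workshop of 8, one time point). The workshop effect cancels from ENTREN-F vs ENTREN, so V = 1 − ICC: 2[1 − Φ(1.96/√0.95)] = 4.4% at ICC 0.05 and 2[1 − Φ(1.96/√0.90)] = 3.9% at ICC 0.10. Against control, each ENTREN arm has DE = 1 + 3 × ICC, or 1.15 and 1.30, so V = 1.075 and 1.15 and the sizes are 5.9% and 6.8%. Simulations agreed: about 4–5% and about 6–7%.

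**The case against.** - **Group delivery is inferred.** This is true. The workshop label, the joint sessions and the confidentiality rule all point to it, and nothing available points to individual delivery of the two programmes, but the documents should say so.
- **The two ENTREN arms may share child sessions.** This is the strongest objection, and it stands as a condition on the point. A reader might infer that any positive ICC makes every between-arm p-value too small, or that ENTREN-F vs ENTREN is always the worst case. The documents do not support either, because they do not say whether child workshops mix arms. Full sharing looks unlikely: the six family sessions exist only in ENTREN-F, and the joint sessions are 3 hours in ENTREN and 2 hours in ENTREN-F. With half the ICC from shared child sessions and half from ENTREN-F family groups, simulation gave about 5.9% at ICC 0.05 and 6.2% at ICC 0.10 for ENTREN-F vs ENTREN, well below the nested figures.
- **Workshop size and ICC are unknown.** This stands. The figures form a range, small at its lower end.
- **A mixed model can carry a workshop term.** It can, so the term is unspecified rather than excluded. But the SAP does not specify one, and Kruskal-Wallis for BMI cannot include it.
- **A stand-alone two-arm test at 5% is not the planned procedure.** This is fair; the Bonferroni and three-arm figures are closer to the plan, and they are inflated too.

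**Conclusion.** The point holds conditionally. As written, the SAP analyses children in the ENTREN arms as independent across workshops. If workshops are nested within arm and the ICC is positive, between-arm p-values are too small. At ICC 0.05 and 8 completers per workshop, the true size is about 7–9% for nominal 5% tests at one time point, and for three-arm Kruskal-Wallis on change about 8–9% at a T0–T1 correlation of 0.5. It is higher on change if that correlation is higher and the workshop effect arises only after T0. If child workshops mix the two ENTREN arms, those sessions do not inflate ENTREN-F vs ENTREN, and only the comparison with control stays mildly inflated.

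All sizes rest on assumed workshop size, ICC, allocation and an unclustered control arm. The change should be made because it costs little in data collection. The documents do not show that the trial's conclusions would be wrong without it.

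**What to change.** 1. State whether sessions are group-delivered, the number and size of workshops, and whether child workshops mix the two arms. Record a workshop identifier for each ENTREN and ENTREN-F child, and a family-group identifier in ENTREN-F if that group differs.
2. Base between-arm comparisons, including BMI, on a mixed model of outcomes from T1 onward with T0 as covariate and a workshop random effect in the ENTREN arms only. Nest it in arm, or let it cross the two ENTREN arms if workshops are mixed. Use Satterthwaite or Kenward-Roger degrees of freedom.
3. If T0 stays as an outcome level, use a workshop-by-time effect. A time-constant workshop intercept cancels from change and leaves the arm-by-time test uncorrected.
4. If the model does not converge and each workshop holds one arm, use T0-adjusted workshop means. In simulation at ICC 0.05 this restored the size of ENTREN-F vs ENTREN to 5.0%.
5. Keep Kruskal-Wallis as descriptive, check model residuals, and report the ICC with its uncertainty.

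**Cost.** One or two identifiers, a variance term and larger standard errors. With DE 1.35, 64 completers carry the information of 64/1.35 = 47. The detectable difference for ENTREN-F vs ENTREN at 80% power (one time point, no baseline adjustment) rises from about 0.50 SD to 3.013 × √(2 × 1.35/64) = 0.62 SD at ICC 0.05. Even at ICC 0 it is 3.013 × √(2/64) = 0.53 SD, because a workshop-level test has only 14 degrees of freedom. With about 8 workshops per arm the ICC will be estimated imprecisely.

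### The SAP's only follow-up rule hangs on a main effect of time, which averages over the arms, and no arm test leads to the between-arm contrasts that the objective needs

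*SAP*

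**What the plan says.** The statistical analysis section of the SAP names three analyses that involve arm:

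- for BMI, "Participant BMI changes over time by group will be measured using a Kruskal-Wallis test";
- for the comparisons in general, "two-way analysis of covariance (ENTREN-F, ENTREN, Control Group) and time (T0,T1, T2 and T3) will be used";
- a mixed model, described as "Mixed model repeated measures analyses of covariance models tested whether intervention effects varied for each type of group".

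One sentence then covers follow-up testing: "In those cases in which we found significance in the global comparisons, we will carried out pairwise comparisons following asignificant main effect of time", with a Bonferroni post hoc test. Significance is set at 0.05.

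The questions come from the protocol. Its objective sets ENTREN-F against ENTREN and against usual treatment. Hypothesis (b) expects improvement in the child outcomes "after both interventions (ENTREN and ENTREN-F programme), in comparison to control group". Hypothesis (d) expects improvement in family outcomes, including "psychological distress of the parents, and the family environment, after the intervention of the ENTREN-F programme", and only there. Hypothesis (e) concerns maintenance: "The significant changes produced will remain stable at the 6, 12 and 18-month follow-up in the ENTREN-F group".

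**The concern.** A main effect of time asks whether the mean over all three arms differs between visits. It does not ask whether arms differ, yet it is the only effect that the follow-up rule names. The global comparisons that start the rule are mentioned once and not defined.

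With three arms, a significant group x time, mixed-model or Kruskal-Wallis result does not show which arms differ. The pairwise step is where the objective and hypothesis (b) would be answered, and it is tied to the wrong effect. Followed literally, the rule can run when arms do not differ, and it can withhold arm comparisons when they do. Read loosely, it leaves the trigger, the visit and the number of comparisons to be settled after the data are seen.

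**Working it through.** **Step 1. What the pairs could be.** The sentence allows three readings.

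| Pairs | Number for Bonferroni | What they address |
|---|---|---|
| Visits T0-T3, pooled over arms | 6, level 0.05/6 = 0.0083 | Change averaged over arms; nothing about arm differences |
| Visits within each arm | 6 per arm | Bears on (d) and (e); does not test one arm against another |
| Arms | 3, level 0.05/3 = 0.0167; or 3 x 3 = 9 if repeated at T1, T2 and T3, level 0.05/9 = 0.0056 | The objective and (b), but a time condition is irrelevant to them |

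The SAP does not say which family its Bonferroni test covers. No reading gives a between-arm contrast that follows from an arm test.

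**Step 2. How far a time effect and an arm effect can part.** The SAP and protocol give no effect size, SD, visit correlation or allocation ratio, so these are assumed. The documents give 240 children and 20% dropout. With equal allocation that leaves 240 x 0.8 / 3 = 64 completers per arm. Further assumptions: visits T0-T3, SD 1, equal correlation between visits, and each shift reached at T1 and held. Shifts are listed as ENTREN-F/ENTREN/control.

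The pooled change is the mean of the three shifts:

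- -0.2/-0.2/-0.2: pooled -0.2, arm difference 0.
- -0.4/0/0: pooled -0.4/3 = -0.13, arm difference 0.4.
- -0.4/-0.1/-0.1: pooled -0.6/3 = -0.2, arm difference 0.3.

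The tests are from a split-plot analysis of variance. Error df are (192 - 3) x 3 = 567. Time is F = MS(time)/MS(error) on 3 and 567 df; group x time is F = MS(group x time)/MS(error) on 6 and 567 df. Each scenario has 10,000 simulated trials, with Monte Carlo error of at most 0.5 points for the rates. The last column is P(group x time significant) multiplied by the share of those trials in which time is not significant.

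| Correlation | Shifts | Time sig. | Group x time sig. | Group x time sig., time not (all trials) |
|---|---|---|---|---|
| 0.7 | -0.2/-0.2/-0.2 | 97% | 5% | not relevant |
| 0.7 | -0.3/0/0 | 43% | 62.5% | 0.625 x 0.574 = 36% |
| 0.7 | -0.4/0/0 | 68% | 89% | 0.891 x 0.319 = 28% |
| 0.7 | -0.4/-0.1/-0.1 | 97% | 63% | 0.626 x 0.031 = 2% |
| 0.7 | -0.5/-0.1/-0.1 | 99% | 89% | 0.889 x 0.006 = 0.5% |
| 0.7 | -0.3/-0.3/0 | 97% | 61% | 0.614 x 0.032 = 2% |
| 0.5 | -0.4/0/0 | 45% | 65% | 0.651 x 0.552 = 36% |
| 0.5 | -0.4/-0.1/-0.1 | 82% | 39% | 0.393 x 0.174 = 7% |
| 0.8 | -0.4/0/0 | 87% | 98% | 0.983 x 0.134 = 13% |

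Under equal drift of -0.2 the pooled T0-T1 comparison, adjusted over six pairs, is significant in 82% of trials although no arms differ.

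Holding the arm difference fixed isolates the effect of the time condition. At a difference of 0.3, blocking falls from 36% (-0.3/0/0) to 2% (-0.4/-0.1/-0.1). At 0.4 it falls from 28% (-0.4/0/0) to 0.5% (-0.5/-0.1/-0.1).

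**Step 3. The within-arm reading.** At correlation 0.7 with -0.4/0/0, a within-arm T0-T1 test at 0.05/6 is significant in 92% of trials in ENTREN-F and about 1% in each other arm, so it does carry information on (d). Under equal drift of -0.2 it is significant in about 27% in every arm. The arms are independent, so ENTREN-F alone comes out significant in about 0.27 x 0.73 x 0.73 = 14% of trials with no arm difference. Separate tests per arm therefore do not replace a contrast between arms.

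**Step 4. Size of the family in a corrected rule.** With no true effect, T0-adjusted contrasts and correlation 0.7, the chance of at least one false result is 12% if all nine arm-by-visit contrasts are tested at 0.05/3, 5% if they are tested at 0.05/9, and 4% for three contrasts averaged over T1-T3 at 0.05/3.

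**The case against.** The strongest defence is that the sentence is loosely drafted. The global comparisons most naturally mean the tests listed just before it, which include arm, and the mention of time may be a slip in a sentence with other language errors. The protocol already names the arms, three arms give only three pairs, and the SAP names Bonferroni. Time comparisons also have a purpose, because the protocol's second aim is maintenance.

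Much of this stands. A reader might infer that the plan contains no test of arm differences; it contains three that involve arm. A reader might infer that the contrasts would be invented after the data are seen; the protocol fixes the arms, and only the trigger, the visit and the adjustment family are open. A reader might infer that a time effect will be reported as an arm effect; the SAP does not say so, and group x time keeps its 5% error rate. Visit comparisons within ENTREN-F are relevant to hypothesis (e).

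The defence does not remove the defect. Even if time is a slip for some other effect, the sentence does not say what the pairs are, and no reading takes the reader from an arm test to the contrasts in the objective and hypothesis (b).

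The simulation is open to fair challenge too. Its effects and correlations are assumed, and it uses complete cases in an analysis of variance, not the planned covariance or mixed models. It illustrates the consequence; the finding rests on the text.

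**Conclusion.** The point holds. The SAP states a follow-up rule aimed at an effect that does not compare arms, and it supplies no route from its arm tests to the between-arm contrasts. It should be corrected before analysis, although the omnibus arm tests themselves are in place.

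Under the assumptions above, at correlation 0.7, the rule as written is met through time in about 97% of trials with equal drift and no arm difference. With a -0.4 SD shift in ENTREN-F only, it would block arm contrasts in about 28% of all trials (36% at correlation 0.5, 13% at 0.8). These two harms belong to different readings of the pairs and should not be added together.

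A reader might take 28% as the general loss. The documents do not support that. It needs the strict pattern of hypothesis (d), with no change in the other arms. It falls to about 2% if those arms also improve by 0.1 SD (-0.4/-0.1/-0.1), which is plausible because ENTREN families attend three joint sessions and control families receive healthy-habit consultations and monitoring.

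**What to change.** Replace the follow-up sentence with a rule that does the following:

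1. Names the global test of arm differences: group x time with T0 kept as a level, or the group effect in a model with T0 as covariate and later visits as responses.
2. Prespecifies ENTREN-F versus control, ENTREN versus control and ENTREN-F versus ENTREN, and states that they do not depend on the time effect.
3. States the visit and the family: Bonferroni over three per outcome if the contrasts are made at one stated visit or averaged over the post-baseline visits, or over nine if made at each of T1, T2 and T3.
4. Keeps time comparisons, made within ENTREN-F, for hypothesis (e), and says that they are not evidence that arms differ.

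The cost is SAP wording and contrast statements in the same software, with no new data. That the SAP's time factor ends at T3 while the protocol schedules a visit "at 12-month follow-up (T_3) and at 18-month follow-up (T_4") is a separate point.

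### The small/medium/large labels for partial eta squared depend on the between-visit correlation and on the term tested, so they cannot be compared across outcomes

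*SAP*

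**What the plan says.** The SAP plans a "two-way analysis of covariance (ENTREN-F, ENTREN, Control Group") by visit, "and time (T0,T1, T2 and T3) will be used", followed by mixed-model repeated-measures analyses of covariance. Pairwise Bonferroni comparisons follow a significant main effect of time. For magnitude, "the effect size will be measured using partial eta squared". The grading is introduced by "The guidelines for interpreting this value are as follows", and the thresholds are "0.14, large effect", "0.06, medium effect" and "0.01, small effect (Cohen, 1988").

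The SAP does not say whether the graded term is time, group or group-by-time. It plans no confidence interval and no between-arm difference in original units. BMI change by group is assigned to a Kruskal-Wallis test, and the SAP does not say whether BMI z also enters the analysis of covariance.

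**The concern.** The cut-offs describe the spread of group means relative to the spread between individuals. In a repeated-measures model, the error term for time and group-by-time is within-child variation only. The more stable an outcome is from visit to visit, the smaller that error, and the larger partial eta squared becomes for an identical change in SD units.

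The protocol's hypotheses cover anthropometry, physical activity, distress, eating pathology and family environment. These are measured by nurses, accelerometers and questionnaires, and there is no reason to expect the same r for all of them. One fixed scale would then rank outcomes partly by their stability rather than by benefit. Because the term is not named and the post hoc tests follow a main effect of time, a change shared by all three arms could also carry a favourable label.

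**Working it through.** **Inputs from the documents.** Cut-offs 0.01/0.06/0.14, three groups and visits T0-T3 (SAP). 240 children and 20% expected dropout (protocol, Participants and Recruitment Procedure).

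**Assumptions.** Equal allocation, so 240 × 0.8 / 3 = 64 per arm. SD 1 at every visit. The same correlation r between any two visits. A step change after T0 that is then held. The documents give no between-visit r for this sample. The only test-retest figure is 0.74 for the CAPS perfectionism scale, from its initial validation, so r is ranged from 0.5 to 0.95.

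**1. Scale of the cut-offs.** For two equal independent groups, d = 2√(η²/(1−η²)). The cut-offs give d = 0.20, 0.51 and 0.81. In reverse, η² = d²/(d²+4) at d = 0.2, 0.5 and 0.8 gives 0.0099, 0.0588 and 0.1379. The cut-offs therefore sit on the independent-groups scale.

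**2. Time effect, 0.2 SD change common to all arms.** With k visits, the population value is A/(A + (k−1)(1−r)), where A is the sum of squared deviations of the visit means.
- Two visits: A = 0.2²/2 = 0.02, giving 0.02/(0.02 + 1 − r).
- Four visits: A = 0.2² × 3/4 = 0.03, giving 0.03/(0.03 + 3(1 − r)) = 0.01/(0.01 + 1 − r).

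**3. Group-by-time, both programmes change 0.3 SD and control 0.** The changes 0.3, 0.3 and 0 have mean 0.2 and variance (0.01 + 0.01 + 0.04)/3 = 0.02.
- Two visits: A = 0.02/2 = 0.01, giving 0.01/(0.01 + 1 − r).
- Four visits: A = 0.02 × 3/4 = 0.015, giving 0.015/(0.015 + 3(1 − r)).

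| Population value | r = 0.5 | r = 0.74 | r = 0.9 | r = 0.95 |
|---|---|---|---|---|
| Time, 0.2 SD, T0-T1 | 0.038 small | 0.071 medium | 0.167 large | 0.286 large |
| Time, 0.2 SD, T0-T3 | 0.020 small | 0.037 small | 0.091 medium | 0.167 large |
| Group-by-time, 0.3 SD, T0-T1 | 0.020 small | 0.037 small | 0.091 medium | 0.167 large |
| Group-by-time, 0.3 SD, T0-T3 | 0.010 small* | 0.019 small | 0.048 small | 0.091 medium |

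*0.015/1.515 = 0.0099, on the border of the lowest cut-off. The second and third rows agree because their formulas happen to coincide.

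**4. Where the label changes (time effect, 0.2 SD).** Setting the formulas equal to 0.06 and 0.14: over two visits, medium starts at r of about 0.69 and large at about 0.88. Over four visits, they start at about 0.84 and 0.94.

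**5. Expected values with 64 per arm.** Sample values average slightly above the population values. Simulation of the four-visit time effect gives about 0.025 (r = 0.5), 0.053 (0.8), 0.096 (0.9) and 0.172 (0.95). For T0-T1, F = 0.2² × 192/(2(1−r)) and η² = F/(F+189). At r = 0.5, F = 7.68 and η² = 0.039. At r = 0.95, F = 76.8 and η² = 0.289. Simulated means are 0.043 and 0.290.

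**6. A measure that does not move with r.** Generalised eta squared keeps the between-child variance in the denominator: (A/k)/(A/k + 1). For the 0.2 SD time effect this is 0.01/1.01 = 0.0099 over two visits and 0.0075/1.0075 = 0.0074 over four, at any r.

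**The case against.** **The correlations are assumed.** This stands. At the one documented test-retest value, 0.74, a 0.2 SD common change is medium over two visits and small over four, and large over four visits needs r of about 0.94. The fault, however, needs only that r differs between outcomes.

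**The treatment term is less affected.** This stands in part. Hypotheses (b) and (d) concern group contrasts. With a 0.2 SD change in both programmes over two visits, group-by-time goes from 0.009 at r = 0.5 (below small) to 0.082 at r = 0.95 (medium), and large needs r of about 0.973. At 0.3 SD it is medium at most over four visits within the assumed range. Over two visits, though, it still spans small to large, so the problem is not confined to the time term.

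**BMI.** A reader might infer that BMI z will be called large and questionnaires small for the same benefit. The documents do not support that: the Kruskal-Wallis test named for BMI change yields no partial eta squared, it is unclear whether BMI z enters the covariance model, and no correlation is given for it.

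**A shared change published as a large treatment effect.** Also tempting, but it would be a large time effect. The SAP leaves the graded term open; it does not say a time effect will be presented as a treatment effect.

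**Only labels are at stake.** True. No test, estimate or sample size changes, and generalised eta squared is partly a matter of preference.

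**Conclusion.** The point holds as a matter of interpretation. The fixed labels depend on an unstated between-visit correlation and an unnamed term, so they are not comparable across outcomes.

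Under equal allocation, 64 per arm, equal correlations and r from 0.5 to 0.95, a 0.2 SD change common to all arms has an expected time-effect value of about 0.025 to 0.17 over T0-T3 and 0.04 to 0.29 over T0-T1: small to large in both cases, with no treatment effect. For group-by-time at 0.3 SD, the population value runs from 0.010 to 0.091 over four visits (small to medium) and from 0.020 to 0.167 over two visits (small to large). The dependence on r follows from algebra; which outcome would receive which label cannot be determined from the documents.

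**What to change.** Drop the fixed small/medium/large labels for within-child terms. For each outcome and each post-baseline visit, report the baseline-adjusted differences ENTREN-F minus control, ENTREN minus control and ENTREN-F minus ENTREN, in original units and divided by the pooled T0 SD, each with a 95% confidence interval. These estimates address the group-contrast hypotheses directly. If an eta-type figure is kept, name the term it belongs to and use generalised eta squared. State which outcomes enter the covariance model, including whether BMI z does.

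The cost is a change of SAP wording and slightly more output, with no new data. Some effects may look less favourable than they would under the present labels.
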